Trans rectal ultrasound is the current standard imaging for the clinical assessment of the prostate gland [29]. Having said that, MRI can provide a more comprehensive assessment of the prostate size and tissue viability. Contrast-enhanced MRI provides a perfusion “map” of the prostate and allows the determination of the extent of infarction (or non-perfusion) of the prostate. The preliminary work in both Lisbon and Sao Paulo suggests that the greater the degree of de-vascularization of the prostate, the greater the volume reduction. This is likely to correlate with symptom improvement, although this requires confirmation. We believe that this study will provide preliminary data that can be used to help design studies to test that hypothesis.

Adverse Events

Each adverse event will be recorded as they occur. Each will be categorized as to type and severity using the Society of Interventional Radiology (SIR) definitions of adverse events based on outcome. That classification is as follows:

Type	Class	Definition
Minor	A	No therapy, no consequence
	B	Nominal therapy, no consequence; includes overnight admission for observation only.
Major	C	Require therapy, minor hospitalization (<48 hours).
	D	Require major therapy, unplanned increase in level of care, prolonged hospitalization (>48 hours).
	E	Permanent adverse sequelae.
	F	Death.

Analysis

The primary outcome is the absence of complications to the bladder, rectum or other pelvic structures detected in the first week after therapy. Each patient will be judged free of these adverse events or not. For those with an adverse event, the complication will be scored using the SIR definitions. Descriptive statistics will be used to summarize these events, along with patient demographics and initial clinical status.

Appropriate parametric and non-parametric tests will be used to assess change in laboratory measures, urine flowmetry parameters, and scores from the IPSS and IIEF. Changes in prostate volumes and the estimated volume of devascularized tissue will be calculated for each patient and outcomes from the different embolics will be compared. Appropriate paired parametric and non-parametric tests will be used to determine statistical significance. A p value of 0.05 will be considered statistically significant.

Statistical Considerations (justification for sample size or “n”, power or degree of change):

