Descriptive statistics will be used to summarize these events, along with patient demographics and initial clinical status.

Appropriate parametric and non-parametric tests will be used to assess change in Q Max flow, IPSS, IIEF and the SF-36. Changes in prostate volumes and the estimated volume of devascularized tissue will be calculated.

Relative importance/value of the trial, considering “standard” therapy and competing trials:

An alternative procedure to surgery with durable results would be beneficial to patients with LUTS who cannot tolerate medical therapy or cannot have surgery performed for other comorbidities.

Feasibility of study including projections for accrual of subjects (Total and Georgetown University) and timeline for accrual:

Anticipated Accrual for local site? 30

Overall Target Accrual? 30

How Long Will Study Be Open to Accrual? _____12-24_____ month(s)

Duration of Study? _____5 years after last recruited patient.

- 6. Risks:** Indicate what you consider to be the risks to subjects and indicate the precautions to be taken to minimize or eliminate these risks. Justify the need for a placebo control group if one is included in this study. Where appropriate, describe the data monitoring procedures that will be employed to ensure the safety of subjects. Use additional sheets as needed.

This is a Phase I-II safety study focused on the local risks in the pelvis of this procedure. While there are other potential risks due to the iodinated contrast, arterial puncture and the passage of the catheters within the vessels, these risks are very low, well less than 5% and no greater than for any other arteriographic procedure. Other potential risks related to an embolization procedure include the risk of conscious sedation and radiation exposure. We anticipate this procedure taking on average about 30 minutes of fluoroscopy and approximately 100 angiographic images. We will use ALARA principles to reduce X-ray exposure, including tight collimation, maximizing tube subject distance, varying angulation of the X-ray beam, slow pulsed fluoroscopy rates and slow filming rates for angiographic series. We will record all available exposure factors for subsequent analysis, as well as patient BMI. The radiation safety officer at Georgetown University Hospital has reviewed our approach and has approved it from a radiation safety perspective.

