We cannot accurately estimate the risk of bladder or rectal injury as detailed analysis of the currently reported patient experience has not been reported. We have visited both the group in Lisbon, who have now treated over 250 patients and the Brazilian group has treated over 70 patients. There have been no serious rectal injuries reported. There has been one injury in the Lisbon group to the bladder that resulted in the need for bladder resection.

Therefore, the current experience would suggest that the risk of complication is low, with the risk of a serious complication is extremely low (less than 1% chance) but that is based on clinical experience and not careful assessment of the rectum and bladder. This is the main focus of our study

Based on the reported data to date and known potential complications of angiographic procedures, the following are potential risks of the procedure:

Related to the embolization of the prostate: Minor or self-limited complications: burning in the urethra, urinary

infection, hematuria, hematospermia, hemorrhage, vasospasm, rectorrhagia, pain in the pelvis, or allergic reaction to embolic material.

More serious complications related to embolization of the prostate: bladder or bladder neck necrosis, possibly requiring surgical resection. Bladder ischemia causing severe pain, but resolving without complication. Other than the one case of surgical resection of the bladder in Lisbon, all reported complications have resolved with minimal or no therapy.

Complications related to angiography: arterial injury, which in rare instances (<1%) can lead to need for surgical repair of the artery, arterial injury in the pelvis, puncture site hematoma and allergic reaction to the contrast media.

Radiation injury to the skin of the buttocks- this complication is not yet reported but is possible with prolonged procedures.

Risk Minimization

As noted above, great care will be taken with the use of X-ray exposure to minimize dose. Similarly, each patient will be evaluated pre-procedure for sedation risk according to the standard of care and will be followed by both the interventional radiology and urology staff physicians.

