Each significant injury to a patient's bladder or rectum will be reported immediately to the IRB staff. Those with lesser injuries will be recorded and followed to resolution. All minor and major complications will be summarized after each set of 10 patients and reported to the IRB. We currently plan to stop the study for re-evaluation of its overall safety if more than 20% of patients assessed after the first 10 patients (and each subsequent group of 10 patients) suffers either a bladder or rectal injury requiring surgical intervention.

We do not believe a data safety and monitoring committee is needed as our urology co-investigators will serve the role of safety monitors. They have a strong incentive to identify injuries, as they do not perform this procedure and it has the potential to compete with traditional therapies. While our urology colleagues are interested in providing alternatives to TURP for their patients, they have no interest in a therapy that is not safe.

7. Does a Data Safety and Monitoring Board exist?

Yes No

[A Data Safety and Monitoring Board, an independent group of experts, will review the data from this research throughout the study. Patients will be told about new information from this or other studies that may affect their health, welfare, or willingness to stay in this study.]

8. Does this study include a Placebo?

Yes No

9. Website Summary: If this is an open clinical trial, recruitment material for clinical trials and information for sponsors about the type of research we do will be posted on the Clinical Trials website. Please create a brief summary, in Layman Terms (8th grade language) of 200 words or less for this protocol outlining the salient features that may be useful to public and health care professionals.

<http://clinicaltrials.georgetown.edu/index.html>

The Departments of Radiology and Urology at Georgetown University Hospital are collaborating on a research study to determine the safety and effectiveness of prostate embolization, a new treatment for men who have enlarged prostate glands and urinary obstruction. Men with urinary obstruction usually have frequent urge to urinate, a weak urine stream, difficulty starting to urinate and may need to urinate numerous times each night.

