10.4.5 Decision Making Criteria and Stopping Rules

In the section below, please describe data safety monitoring criteria for decision-making regarding continuation, modification, or termination of the clinical study.

The study will be stopped if any two patients in any 10 patients suffer either a bladder or rectal injury requiring surgical intervention. Thus if in the first 10 patients, two patients have this type of injury, the study will be stopped. Similarly, if two patients in any set of 10 patients has this type of injury, the study will be stopped. After each 10 patients, a report on complications will be submitted to the IRB.

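### A single procedure-related death triggers no prespecified pause, because the only halt rules count bladder or rectal injuries requiring surgery

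*Combined protocol and SAP*

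**What the plan says.** Section 10.4.5 gives the stopping rule: "The study will be stopped if any two patients in any 10 patients suffer either a bladder or rectal injury requiring surgical intervention". Section 6 (Risks, under Risk Minimization) has a second version, which halts the study for re-evaluation if more than 20% of a group of 10 "suffers either a bladder or rectal injury requiring surgical intervention". The thresholds differ but the event counted is the same.

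The Adverse Events section sets out the SIR severity scale. Its two highest classes are E ("Permanent adverse sequelae") and F (death). The Analysis section uses the classes to score and describe events. Neither halt rule refers to them.

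On reporting, Section 10.2, whose heading names the death of a subject, requires adverse events to go to the IRB. Sections 6 and 10.4.6 add an immediate report for significant bladder or rectal injury, which 10.4.6 defines as needing surgery. For the rest: "All minor and major complications will be summarized after each set of 10 patients and reported to the IRB".

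On oversight, Section 6 states: "We do not believe a data safety and monitoring committee is needed as our urology co-investigators will serve the role of safety monitors".

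**The concern.** Section 10.4.5 is where the plan sets its criteria for continuing, modifying or ending the study. Followed as written, it lets treatment continue after a man dies from the procedure. A death from another listed risk, such as arterial injury, a contrast reaction or sedation, is not counted. A death from a bladder injury that had been operated on counts as one event, and one event does not stop the study.

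This matters more here than in many small studies. Safety is the primary goal, there is no committee outside the study team, and Section 6 says the risk of bladder or rectal injury cannot yet be estimated accurately. With monitoring kept inside the team, a written trigger decides in advance what happens on a bad day. Without one, whether further men are treated before the death is reviewed depends on someone choosing to pause.

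**Working it through.** The plan states no operating characteristics for its stopping rule, so there is no figure to reproduce. The check has two parts: what each provision does after one procedure-related death, and how large the gap is.

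**Provisions side by side, after one procedure-related death**

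| Provision | Counts the death? | Requires a pause? |
|---|---|---|
| 10.4.5, two in any 10 | Only if it followed a bladder or rectal injury requiring surgery | No: one is below two |
| Section 6, more than 20% of 10 (at least 3 of 10) | Same condition | No: one is below three |
| 10.2, adverse event reporting | Yes | No: a report, with no timeline in the available text |
| 10.4.6, immediate IRB report | Only if it is a bladder or rectal injury requiring surgery | No: a report |
| Sections 6 and 10.4.6, summary after each 10 patients | Yes | No: no threshold attached |

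**Patients still to be treated in the set**

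Inputs: sets of 10 (Sections 6 and 10.4.5). Assumptions: patients are treated one after another, the death is recognised before the next patient is treated, it is equally likely at each position in the set, and nobody pauses.

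- Patients left after the event: 9, 8, ..., 0.
- Mean: (9 + 8 + ... + 0)/10 = 45/10 = 4.5. Maximum: 9.
- Time per set at even accrual of 30 patients: 10/30 × 12 months = 4 months; 10/30 × 24 months = 8 months. The accrual period is 12 to 24 months in the feasibility item; Duration of investigation aims for under 12.

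These counts run to the next scheduled summary. They do not fit class E events, because permanence may be established only at a later visit.

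**Chance that a single-death trigger would fire**

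Inputs: n = 30 (Duration of investigation). The documents give no death rate, so the true rate p is assumed. Section 6 gives an upper reference for all serious complications together: "the risk of a serious complication is extremely low (less than 1% chance". With independent patients, the chance of at least one event is 1 − (1 − p)^30:

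- p = 0.1%: 1 − 0.999^30 = 3.0%
- p = 0.2%: 1 − 0.998^30 = 5.8%
- p = 0.5%: 1 − 0.995^30 = 14.0%
- p = 1%: 1 − 0.99^30 = 26.0% (ceiling only)

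**Check on the ceiling**

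Section 6 cites over 250 patients in Lisbon and over 70 in Brazil, and says: "Other than the one case of surgical resection of the bladder in Lisbon, all reported complications have resolved with minimal or no therapy". Reading this as 0 deaths in 320, the one-sided 95% upper bound is 1 − 0.05^(1/320) = 0.93%. At that rate the chance in 30 patients is 1 − (1 − 0.0093)^30, about 24%. This assumes complete reporting, which Section 6 itself cautions about.

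**Why one event and not two**

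Suppose deaths were instead counted under a two-in-10 rule. With q = P(at least 2 of 10), the chance over three separate sets is 1 − (1 − q)^3. That gives 0.01%, 0.05%, 0.33% and 1.27% at the four rates above. Such a rule would almost never act on a death.

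**The case against.** The best defence is that the pelvic scope was chosen and explained: "This is a Phase I-II safety study focused on the local risks in the pelvis of this procedure". Section 6 rates the other procedural risks as no greater than for any arteriographic procedure, and the documents report no death after prostate embolization. A death would have to be reported to the IRB under 10.2, and that duty is not tied to the 10-patient summaries. Section 10.4.7 likewise takes withdrawals linked to significant injury out of batch reporting. Any responsible team would probably stop and look.

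Much of this stands. The event is unlikely, and discretion may well work. But a local focus does not explain omitting death, and a duty to report is not a duty to pause.

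A reader might infer more than the documents support:

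- **That the plan obliges the team to carry on after a death.** It does not. Nothing in the available text forbids a pause.
- **That no class E or F event counts at all.** Not so. One that is a bladder or rectal injury requiring surgery counts as one event toward the rule.
- **That nine more men would be treated before the IRB hears.** Nine is the maximum left in a set if nobody pauses, and 10.2 reporting does not wait for the set to finish.
- **That the chance of a death is 26%.** That figure applies a ceiling stated for all serious complications to deaths alone.
- **That permanent injury needs the same automatic trigger.** Class E has no severity floor, and permanence may be judged months later. A pause could come late or for a mild effect.

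**Conclusion.** The concern holds for death. On the available text, neither halt rule makes a single procedure-related death a reason to pause, and a death outside the bladder-or-rectum surgical definition is not counted. This is a gap in an explicit safety rule. It does not affect any estimate or analysis.

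The practical size is an average of 4.5 and at most 9 patients left in the set after a promptly recognised death, unless someone chooses to pause. The lower assumed rates, giving 3.0% to 5.8% over 30 patients, are the more relevant ones for death, but they remain assumptions.

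One limit applies: the part of the safety-monitoring section between 10.2.1 and 10.4.4 was not in the text reviewed. Section 10.4.5, on stopping rules, was. The change is worth making, with medium confidence in its practical weight.

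**What to change.** Add this to Section 6 (Risk Minimization) and Section 10.4.5, alongside the existing rule:

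*After any single death judged possibly related to the procedure by the urology safety monitors (SIR class F), no new patient will be enrolled or embolized and the IRB will be told immediately. Treatment resumes only after IRB review. Follow-up of patients already treated continues.*

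The last sentence matters: cystoscopy, imaging and visits for treated men must not be suspended just after a serious event. Naming the urology monitors settles who makes the relatedness call.

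Optionally, a major permanent injury to a pelvic structure (SIR class E) can be a second trigger once judged permanent, on the understanding that this pause may come late.

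The cost is one statement in two places. It needs no new data, since the SIR class is already recorded. The downside is a small chance of a temporary pause: 3.0% to 5.8% over 30 patients if possibly related deaths occur at 0.1% to 0.2%.

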10.4.6 Monitoring of the Study

In the section below, indicate who will monitor the study and to whom the study will report. Describe the frequency of the monitoring. If a DSMB is required, describe the composition of the board, its role, and the frequency of meetings and methods of communications.

The urology staff will serve as safety monitors. Each significant injury (requiring surgical intervention) to a patient's bladder or rectum will be reported immediately to the IRB staff. Lesser injuries will be recorded and followed to resolution. All minor and major complications will be summarized after each set of 10 patients and reported to the IRB.

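### The stopping rule for surgical injuries does not settle which ten men are counted together, so injuries in patients 10 and 11 stop the study on one reading and not on another

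*Combined protocol and SAP*

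**What the plan says.** The rule appears in two places in the combined protocol and SAP.

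- **10.4.5, Decision Making Criteria and Stopping Rules:** "The study will be stopped if any two patients in any 10 patients suffer either a bladder or rectal injury requiring surgical intervention". The only worked case is the first ten: "Thus if in the first 10 patients, two patients have this type of injury, the study will be stopped". Later men are covered by "Similarly, if two patients in any set of 10 patients has this type of injury, the study will be stopped". It does not say how those later sets are formed or when the count is made.
- **Item 6, Risk Minimization:** the study stops for re-evaluation "if more than 20% of patients assessed after the first 10 patients (and each subsequent group of 10 patients) suffers" an injury of this kind. This points to successive tens assessed when each is complete, but with a different threshold.

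Section 10.4.6 uses the same word, set, for its reporting tens: "All minor and major complications will be summarized after each set of 10 patients and reported to the IRB". Injuries requiring surgery to the "bladder or rectum will be reported immediately to the IRB staff. Lesser injuries will be recorded and followed to resolution". Item 6 says that a monitoring committee is not needed, because "our urology co-investigators will serve the role of safety monitors". It puts current experience at a low risk overall, "with the risk of a serious complication is extremely low (less than 1% chance", while also saying that bladder and rectal risk cannot be accurately estimated.

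**The concern.** Safety is the primary goal, and in the text available this rule is the only stop tied to surgical injuries. Three windows fit the words: successive tens, any ten consecutive men, or any ten of the men treated. The last amounts to stopping at the second injury anywhere. If the investigators and the IRB hold different readings, the same two injuries can call for a halt under one and not under the other.

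Following the item 6 grouping as written has two consequences. Two injuries on either side of a boundary do not count together, and two early injuries within a ten need not be acted on until that ten is complete.

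**Working it through.** The plan states no operating characteristics for the rule, so there is no figure to reproduce.

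**Inputs.** 30 patients (Duration of investigation); a count of two (10.4.5). Assumptions: injuries are independent with a common rate p; each is known before the next man is treated; p is 10%, 5% or 1%. A halt is counted only up to patient 29, because a halt after patient 30 spares nobody.

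**The example.** Injuries in patients 10 and 11 give one in 1-10 and one in 11-20, so there is no stop under successive tens. Patients 2-11 are ten consecutive men holding both, so a rolling ten stops. Any ten men including both also stops.

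**All possible pairs.** Two injured men among 30 can be chosen in 30 × 29 / 2 = 435 ways.
- Successive tens stop for 3 × 45 = 135 (31%).
- A rolling ten needs the two at most nine places apart: the sum of (30 − d) for d = 1 to 9 is 270 − 45 = 225 (52%).
- Any ten men: all 435.

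**Chance of a halt by patient 29.** Let q(n) be the chance of at most one injury in n men: (1 − p)^n + n p (1 − p)^(n−1).

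- Successive tens, checked at each injury: 1 − q(10)² q(9). At 10%, q(10) = 0.7361 and q(9) = 0.7748, giving 1 − 0.4198 = 0.580.
- Any ten consecutive men, checked at each injury: there is no halt only if all injuries lie at least ten places apart. Among 29 men there are 1, 29, 190 and 165 such patterns with 0, 1, 2 and 3 injuries. At 10% the chance of no halt is 0.9^29 + 29(0.1)(0.9^28) + 190(0.1²)(0.9^27) + 165(0.1³)(0.9^26) = 0.0471 + 0.1518 + 0.1105 + 0.0107 = 0.320, so a halt has chance 0.680.
- Second injury among all men: 1 − q(29). At 10%, 1 − 0.1989 = 0.801.
- Successive tens, checked only after 10 and 20 men: 1 − q(10)². At 10%, 1 − 0.5418 = 0.458.

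| Reading | 10% | 5% | 1% | Mean men treated at 10% |
|---|---|---|---|---|
| Successive tens, each injury | 58% | 22% | 1.2% | 20.8 |
| Any ten consecutive, each injury | 68% | 30% | 1.9% | 19.1 |
| Second injury among all men | 80% | 43% | 3.4% | 17.7 |
| Successive tens, after 10 and 20 only | 46% | 16% | 0.9% | 22.8 |

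The first three rows isolate the window. At a 10% rate, moving from successive to rolling tens adds 10 percentage points, and dropping the window adds another 12. The first and last rows isolate timing: checking only at the end of each ten loses 12 points (58% − 46%).

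**The case against.** The strongest reply is that the documents already point one way. Every group they actually describe is a successive ten: the first ten in 10.4.5, the later groups in item 6, and the reporting sets in 10.4.6. The any-ten-men reading makes the number ten redundant and is the least likely intent. This stands as a lean. It does not settle the matter, because 10.4.5 says any ten and any set, and item 6 is a competing version with a different threshold (more than 20%, so three of ten, against two of ten).

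A reader might infer that the choice of window moves the chance of a halt from 46% to 80% at a 10% rate. It does not: that span mixes the window with the timing of the check. A reader might also infer that the plan gives no timing at all. Item 6 does tie the assessment to completed tens; only 10.4.5 is silent.

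Each surgical injury goes to the IRB at once, so injuries in patients 10 and 11 would both be before it. That is a real safeguard, and it means opposite decisions are possible rather than shown. But no pause or stop is attached to the report, and the IRB would have the same unclear rule to apply.

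Finally, the threshold conflict is the larger problem. With successive tens over all 30 men at a 10% rate, two of ten stops with chance 60.1% and more than 20% with chance 19.6%. Resolving the threshold would still leave the window open.

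**Conclusion.** The point holds as an unresolved conflict of wording in an operative safety rule. The text leans towards successive tens without settling it, and the decision on injuries in patients 10 and 11 depends on the reading. With timing held fixed at each injury, the halt chance runs from 58% to 68% to 80% at a 10% rate and from 22% to 30% to 43% at 5%.

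At 1% it runs only from 1.2% to 3.4%, so under the risk the protocol expects the practical effect is small. The case for acting is that the rule exists for the event that this expectation is wrong. The documents do not support a claim that the second-injury reading is the intended one, or that surgical injuries would go unnoticed.

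The figures rest on independent injuries, a count of two, and each injury being known before the next man is treated. The three rates are assumptions, not estimates from the plan.

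**What to change.** In 10.4.5 and item 6, at the same time as the threshold conflict is resolved, state one rule checked at each new surgical injury: stop treatment for IRB re-evaluation when two bladder or rectal injuries requiring surgical intervention have occurred within any 10 consecutively treated patients. This keeps the authors' ten-patient window and removes the boundary. A more cautious alternative, without a window, is to stop at the second such injury among all men treated. That goes further than clarification, since it gives up the window.

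The cost is one or two sentences, with no new visits or tests. At a 1% true rate the false-stop chance by patient 29 is 1.9% (3.4% for the alternative), against 0.9% to 1.2% under successive tens.
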